## **Introduction**

Recovery after an injury or surgery relies on successful wound healing. Poor wound healing can increase the risk of infection, patient discomfort, morbidity, and mortality (Eming & Tomic-Canic, 2017; Gouin & Kiecolt-Glaser, 2011). Not only are there direct patient impacts, but poor wound healing can also put extra strain on the healthcare system by increasing the length of hospital stays and therefore costs related to hospital care (Broadbent et al., 2003; Eming & Tomic-Canic, 2017; Robinson et al., 2017). As a process of healing disrupted tissue, wound healing involves the stages of clot formation, inflammation, proliferation, and remodelling (Irwin & Vedhara, 2007). The duration and success of healing at each stage depend on the immune system's functioning, which is vulnerable to the effects of psychological variables, including stress (Walburn et al., 2009).

Stress can work through several fundamental mechanisms to adversely impact wound healing processes (Gouin & Kiecolt-Glaser, 2011; Walburn et al., 2009). Psychological stress is the imbalance between a high demand on a person and a low perceived ability to cope (Cox & Mackay, 1976). Stress activates the hypothalamic-pituitary-adrenal (HPA) and sympathetic-adrenal-medullary (SAM) axes in the body, which release catecholamines (epinephrine and norepinephrine) and glucocorticoids (cortisol). These stress hormones have immunosuppressant effects on the cytokines and growth factors available to regulate each stage of wound healing. The cascading effects from these disturbances prolong the wound healing process and increase the risk of problems, including infections (Glaser et al., 1999; Kiecolt-Glaser et al., 2005; Li et al., 2007; Rodriguez et al., 2008). Stress also has indirect effects on wound healing by increasing poor health behaviours such as smoking, alcohol, poor diet, lack of sleep or exercise, and non-adherence to medication (Robinson et al., 2017).

As stress can impair the wound healing process, several studies have investigated whether psychological interventions can reduce stress and improve wound healing. Psychological interventions can reduce physiological arousal, stress, and anxiety and alter patients' health behaviours and expectations of recovery and pain (Robinson et al., 2017). Systematic reviews by Robinson and colleagues (2017) and Geers and colleagues (2018) support the hypothesis that wound healing can be positively affected by a range of different psychological interventions including relaxation (Broadbent et al., 2012; Gouin, 2008; Han, 2002; Holden-Lund et al., 1988; Rice et al., 2001; Robinson et al., 2015), expressive writing (Koschwanez et al., 2013; Weunman et al., 2008), social support (Ginandes, 2003; Robles 2007) and yoga (Oswak et al., 2011; Rao et al., 2008).

Of these interventions, relaxation was found the most beneficial for wound healing outcomes (Robinson et al., 2017). Relaxation interventions can include deep breathing, guided imagery, biofeedback, and progressive muscle relaxation techniques. These techniques aim to counterbalance the stress response by reducing autonomic arousal and lowering stress hormones at the wound site, resulting in improved healing (Jacobs, 2001; Robinson et al., 2015). Relaxation interventions have been found to significantly increase the amount of collagen deposition (Broadbent et al., 2012), lower erythema (Holden-Lund et al., 1988), increase peripheral perfusion in foot ulcers (Rice et al., 2001), induce faster healing of stomach ulcers, and increase skin barrier recovery rates (Robinson et al., 2015). These findings demonstrate that relaxation is associated with better wound healing in a variety of different wound types.

Traditional methods of audiotapes and human-led relaxation are the most studied delivery method. Audiotapes are instructional and can be used from home, but they only provide passive information and guidance. Unlike audiotapes, human involvement can add

social support, interaction, accountability, and feedback while guiding patients through a relaxation script and teaching relaxation techniques. Studies in other health conditions such as tension headaches have found that audiotaped instructions and treatment manual are more cost-effective and are comparable at reducing headaches compared to therapist-led or supported relaxation sessions (Teders et al., 1984). However, there is no research comparing delivery methods for reducing stress and wound healing.

Due to the increasing strain on the healthcare system from overpopulation, understaffing, lack of resources and the recent COVID-19 pandemic, it is not feasible for all patients to access and afford human-led interventions (Bradbury et al., 2014; Fagherazzi et al., 2020). It is, therefore, crucial that effective health interventions, such as relaxation can be delivered remotely. Patients are already beginning to use mobile apps and the internet to access healthcare, including relaxation and stress management. Relaxation instructions on the internet include online relaxation programs (Alfonsson et al., 2015), computer administration (Carbring et al., 2007), audio tracks available on YouTube, Soundcloud and Google Drive platforms (Cancer Society NZ, 2021), guided audio clips on a website (Pizzoli et al., 2020), and mobile applications (Weekly et al., 2018). Taking advantage of technology for healthcare can offer a delivery approach that is affordable, easily accessible and integrated alongside existing healthcare practice, and can reduce healthcare burden, provide support for the most vulnerable patients and be a safe alternative to human-led relaxation during a pandemic (Bradbury et al., 2014; Fagherazzi et al., 2020; Murray et al., 2016).

As a novel digital health intervention, digital humans are a form of embodied conversational agent (ECA) that includes a computer-based dialogue system and a virtual embodiment (Cassell et al., 2000; Sagar et al., 2014). A virtual embodiment refers to an animated face or body presented on a computer screen. Digital humans use artificial

intelligence in the form of neural networks to learn and respond to user input, such as human facial expressions, movement, and speech (Loveys et al., 2020; Sagar et al., 2016).

Digital humans may have additional benefits to audiotapes because of their multimodal emotional expression and virtual embodiment features. Through multimodal emotional expression, digital humans may provide social and emotional engagement and support (Loveys et al., 2020). Other ECAs have been found to have a greater social presence than disembodied social agents (Lee et al., 2006) and similar social presence to physically embodied agents (Thellman et al., 2016) suggesting that the virtual embodiment of digital humans may increase social presence during the delivery of relaxation.

There is also the opportunity for digital humans to become digital therapists to deliver health or mental health interventions, such as Cognitive Behavioural Stress Management (CBSM; Loveys et al., in prep), cognitive behavioural exercises for loneliness and stress in older adults (Loveys et al., in prep) or medical interviews (Micoulaud-Franchi et al., 2016). The features of digital humans are likely to increase social presence, detect emotions, be supportive and provide feedback, which could then help people to form relationships with the digital human. Together, this may provide a delivery method that could be more engaging, naturalistic, and interactive than a website, mobile app, or audiotape. Digital humans are a practical delivery method as their benefits are similar to human-led delivery but without the cost, poor accessibility and safety issues.

Because digital humans are increasingly being used to deliver healthcare interventions, it is important to test whether they can effectively reduce stress by giving relaxation instructions. This study will measure stress reduction and its effects in several ways, including self-reports, biological and physiological indices, and wound healing. Wound healing offers an outcome that reflects the functioning of the immune system and is also

clinically relevant. Including immunological measures such as skin barrier recovery (SBR) and multiple stress measures in the current study will further understand the underlying mechanisms through which relaxation works on wound healing. The knowledge gained from this study will help determine whether digital humans, as an accessible, affordable, engaging, and naturalistic delivery method, effectively reduce stress and improve wound healing. This new knowledge can then help improve health outcomes in patients with wounds to reduce the risk of infection, mortality and patient discomfort. If digital humans are similar or more effective than audiotapes in delivering relaxation in a healthy population, future research could investigate the feasibility of using digital humans in clinical or vulnerable populations and different cultures.

## **Aims**

The primary aim of this study is to investigate the effects of different delivery methods of a brief relaxation intervention, including audiotapes, a digital human and magazines (control), on wound healing, as indexed by SBR after tape stripping.

The secondary aim is to investigate whether stress reduction (biological, physiological and self-reported) mediates the relationship between relaxation and wound healing.

The tertiary aim is to investigate the effects of different delivery methods of a brief relaxation on levels of anxiety, pain, stress and relaxation (psychological measures) and the level of engagement, satisfaction, and opinions of the digital human delivery in comparison to the audiotape delivery.

## **Hypotheses**

1. It is hypothesised that both the digital human and audiotape conditions will have improved SBR after a tape-stripping wound, as assessed by trans-epidermal water loss (TEWL), compared to the control group, who did not receive a relaxation intervention (only magazines).
2. It is hypothesised that there will be no differences in SBR after a tape-stripping wound, as assessed by TEWL, between the digital human and audiotapes condition.
3. It is hypothesised that the relationship between relaxation and SBR will be mediated by levels of stress (biological, physiological, and self-reported) .
4. It is hypothesised that the digital human condition will have greater improvements in anxiety, stress, pain and relaxation levels and better compared to the audiotape delivery and magazines (control group).

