## **Method**

### ***Study design.***

This randomised controlled trial will use a 3 (time-point) x 3 (condition) mixed factorial experiment to investigate the effects of different delivery methods (digital human v audiotape v control) of relaxation on SBR after tape-stripping.

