### ***Participants***

**Inclusion criteria.** Participants will be eligible for inclusion if they are over the age of 18 and can speak, read, and write in fluent English.

**Exclusion criteria.** Participants will be excluded from the study if they are allergic to adhesive tape, have any inflammatory skin diseases/immunological-related health problems,

are taking medication that affects immune functioning (e.g., prednisone), are pregnant, over the age of 60 or have hearing difficulties or vision loss.

**Sample size.** The sample size was calculated using G\*Power (Faul et al., 2007) with a *mixed factorial ANOVA*. A power level of .80 and a two-tailed significance level of  $\alpha = .05$  was chosen, with an expected effect size of  $f = 0.30$ , based on previous research investigating a relaxation intervention on SBR (Robinson et al., 2017). Using these parameters gives a required sample size of 75. Like previous tape-stripping studies, this will be increased by 20% to account for possible errors in the TEWL measurements (Law et al., 2020), giving a final sample size of 90 participants (30 participants per group).

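### The printed power of .80 describes an omnibus F test with repeated measures; for hypothesis 1 (both relaxation arms better than control) power at the same f is about 44% to 66% at 75 and 54% to 75% at 90

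*Protocol*

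**What the plan says.** - **Protocol, Hypotheses.** Hypothesis 1 is that "both the digital human and audiotape conditions will have improved SBR after a tape-stripping wound" compared with the magazine control. Hypothesis 2 expects no difference in SBR between the two relaxation arms.
- **Protocol, Study design.** The trial is a "3 (time-point) x 3 (condition) mixed factorial experiment".
- **Protocol, Participants (Sample size).** G\*Power was used for a mixed factorial ANOVA with power .80, two-tailed alpha .05 and a Cohen's f of 0.30 taken from earlier SBR work. "Using these parameters gives a required sample size of 75"; "this will be increased by 20% to account for possible errors in the TEWL measurements", giving 90, or 30 per group. The paragraph does not say which F test was powered or what correlation between repeated measures was used.
- **Protocol, Primary outcome measures.** The TEWL readings at the three time-points are combined by formula into one SBR percentage per site.
- **Protocol, Analysis.** SBR is analysed by a mixed factorial ANOVA and by an ANCOVA with covariates such as age, number of tape strips and barrier impairment. No arm-versus-control contrast is named.

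**The concern.** The only power figure in the protocol sits beside a primary hypothesis that it does not describe. An omnibus F test asks whether the three condition means are all equal, and it can be significant when only one relaxation arm differs from control. Hypothesis 1 asks for more. In addition, the repeated-measures calculation credits three measurements per person to an outcome that yields a single score.

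Two things are at stake. First, a reader would take .80 as the chance of confirming hypothesis 1 if relaxation works as assumed, when the chance is lower. Second, the likely alternative result is easy to misread. If the two arms are truly equal, one may still reach p < .05 while the other does not, and this could be reported as one delivery method working and the other failing.

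**Working it through.** **Inputs from the protocol:** k = 3 groups, m = 3 time-points, f = 0.30, two-tailed alpha .05, N = 75 and 90 (25 and 30 per arm).

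**Assumptions not in the protocol:** correlation between repeated measures ρ = 0.5; normal SBR; error variance pooled over three groups; no covariates; equal true effects in the two relaxation arms (the pattern hypothesis 2 expects).

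**1. Reproduce the printed figure.** Between-groups test in a repeated-measures ANOVA: λ = f²·N·m / (1 + (m − 1)ρ), with 2 and N − 3 df.
- N = 75: λ = 0.09 × 75 × 3 / 2 = 10.125; power 0.803.
- N = 90: λ = 12.15; power 0.876.

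The smallest balanced N reaching 80% is 75. The other tests tried gave 27 (group-by-time interaction), 21 (within factor), 84 (between factor, two measurements) and 111 (one-way ANOVA). The result depends on ρ: 0.4 gives 69, 0.6 gives 84 and 0.7 gives 90.

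**2. Omnibus test on one SBR score per person.** λ = f²·N.
- N = 75: λ = 6.75; power 0.619.
- N = 90: λ = 8.10; power 0.707.

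**3. Translate f into an arm-versus-control difference.** For means (d, d, 0) and equal groups, f = d√2/3, so d = 3f/√2.
- Single-score scale: d = 3 × 0.30 / 1.414 = 0.636.
- Scale of the printed calculation: effective f = 0.30 × √1.5 = 0.367, so d = 0.779.

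**4. Power for both contrasts,** each at two-sided .05, sharing one control group (simulation, 2,000,000 runs; numerical integration agrees):

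| Analysed | One contrast, d = 0.636 | Both, d = 0.636 | One contrast, d = 0.779 | Both, d = 0.779 |
|---|---|---|---|---|
| 72 | 58% | 42% | 76% | 63% |
| 75 | 60% | 44% | 78% | 66% |
| 90 | 68% | 54% | 85% | 75% |

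The 72 row is 90 × 0.8, the case in which 20% of the 90 are lost to the TEWL errors the allowance is meant to cover.

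**5. Split the gap at 75.** 80.3 to 61.9 is 18.4 points, from treating a single-score outcome as three repeated measures. 61.9 to 44.4 is 17.5 points, from requiring both contrasts. Together: 35.9 points.

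**6. Chance that exactly one arm is significant although the two are equal** (d = 0.636): P(at least one) − P(both).
- N = 75: 76.1 − 44.4 = 31.7%.
- N = 90: 82.9 − 53.8 = 29.1%.

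**7. Combined relaxation versus control** (weights ½, ½, −1), d = 0.636: noncentrality = d / √(1.5/n).
- n = 25: 2.60; power 73%.
- n = 30: 2.85; power 80%.
- n = 30, only one arm effective: the contrast is d/2 = 0.318, noncentrality 1.42; power 29%.

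**8. Sensitivity.**
- If f = 0.30 came from equally spaced means with audiotape halfway, both-arms power on the single score would be 23% at 75 and 28% at 90.
- If f = 0.30 is an unadjusted effect and the ANCOVA covariates explained an assumed 10%, 30% or 40% of the variance, both-arms power at 90 with no loss would be about 59%, 73% or 81% (covariate df ignored).

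**The case against.** **The protocol claims .80 only for a mixed factorial ANOVA.** This stands. The 75 reproduces for such a test and 75 × 1.2 = 90. A reader might infer that the sample-size arithmetic is wrong; it is not. The fault is that the one printed figure does not describe the primary hypothesis.

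**No decision rule is written.** This also stands. A reader might infer that the trial formally succeeds only if both contrasts reach p < .05. The protocol says no such thing, and contrasts are commonly left to an analysis plan. But *both* is the plain wording of hypothesis 1, and no later plan can make 75 deliver .80 for it under the protocol's own f without a further assumption such as a covariate gain.

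**Setting 80% against 44% mixes two scales.** Correct. A reader might attribute the whole 36-point gap to the both-arms requirement. About half belongs to the repeated-measures assumption; on the scale of the printed calculation, both-arms power falls short of .80 by about 14 points at 75 and 5 at 90.

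**The planned ANCOVA could recover power.** Possibly, and a strong enough covariate effect would reach 80% at 90. The protocol gives no R-squared, so this cannot be credited. Equally spaced means would move the figures the other way.

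**Two contrasts might seem to need a multiplicity penalty.** Not if the claim requires both. Each can then be tested at .05 without adjustment, and no further loss should be charged.

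**Conclusion.** The point holds in limited form. The printed .80 is an omnibus figure under an unstated repeated-measures assumption and does not describe hypothesis 1. Reading *both* as two contrasts at two-sided .05, with equal true effects and no covariates, power is about 44% at 75 and 54% at 90 if f = 0.30 applies to one SBR score per person. It is about 66% and 75% on the scale that produced the printed figure, and about 42% and 63% with 72 analysed. The single-score scale fits this outcome better, because SBR has no time factor and f is attributed to SBR research, but the protocol does not state the scale of f, so the range should be shown. None of the no-covariate scenarios checked reaches 80% at 75 or 90; that would take about 150 participants on the single score, or about 99 on the repeated-measures scale.

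**What to change.** 1. In the sample-size paragraph, state that .80 refers to the omnibus between-groups test, and give the number of repeated measures and the correlation assumed.
2. In the same place, state the power for hypothesis 1 at the same N as a range: about 44% to 66% at 75, 54% to 75% at 90, and 42% to 63% at 72 analysed. List the assumptions: two contrasts at two-sided .05, equal true effects, no covariates, and the two scales for f. If a gain from the ANCOVA is to be claimed, give the R-squared and its source.
3. Add that one significant and one non-significant arm does not show that the delivery methods differ. With equal arms and f = 0.30 on the single score, that split occurs in about 29% to 32% of trials.
4. Optionally, report the combined relaxation-versus-control contrast as an additional test (about 73% power at 75 and 80% at 90, single score). It should not be a required first step: it does not raise the chance of confirming both arms, and it has only about 29% power at 90 if one arm works.

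The cost is wording only, with no extra participants or measurements. The price is a less favourable stated power for the primary hypothesis.

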### *Analysis*

A mixed factorial ANOVA will be conducted to assess differences in SBR between conditions, in addition to an ANCOVA (to control for covariates related to SBR rates such as age, number of strips of tape, and levels of skin barrier impairment; Law et al., 2020; Robinson et al., 2017). For the secondary outcomes (biological, physiological, and psychological measures), mixed factorial ANOVAs will be conducted to analyse the main and interaction effects of time-point and condition. The data will be checked for violations of the normality assumption before analysis. To investigate whether psychological and physiological stress levels mediate the relationship between the delivery condition and SBR, separate exploratory mediational analyses will be conducted.

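### Hypothesis 2 predicts no SBR difference between digital human and audiotape, but the plan has only difference tests and no margin, and 30 per arm leaves most of the relaxation benefit inside the confidence interval

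*Protocol*

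**What the plan says.** Hypothesis 2 (Protocol, Hypotheses) concerns the primary outcome and the comparison of the new delivery method (digital human) with the established one (audiotape): "It is hypothesised that there will be no differences in SBR after a tape-stripping wound". It attaches no size to the absence of a difference.

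The Analysis section says of this outcome: "A mixed factorial ANOVA will be conducted to assess differences in SBR between conditions". It adds an ANCOVA with covariates such as age, number of tape strips and level of barrier impairment. It gives no equivalence or non-inferiority test and no confidence-interval criterion.

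The Sample size paragraph (Participants) is built on detecting a difference: "A power level of .80 and a two-tailed significance level of" 0.05, with f = 0.30 "based on previous research investigating a relaxation intervention on SBR". It continues "Using these parameters gives a required sample size of 75", and "this will be increased by 20% to account for possible errors in the TEWL measurements", which gives 90 participants, 30 per group. No sample size is given for Hypothesis 2.

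The Introduction says where a finding of similarity could lead: "If digital humans are similar or more effective than audiotapes in delivering relaxation in a healthy population", later work could examine feasibility in clinical or vulnerable populations.

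**The concern.** A test for a difference can reject equality but cannot establish it. The plan sets no margin and has no interval-based criterion, so the only result it could produce that might be taken to support Hypothesis 2 is a non-significant comparison. Noise works in favour of that result: fewer usable TEWL readings or a larger SD make non-significance more likely. At stake is whether the trial may describe the digital human as similar to the audiotape for wound healing when its data may also be compatible with losing most of the relaxation benefit.

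**Working it through.** **Inputs from the protocol.** f = 0.30; two-tailed alpha 0.05; power 0.80; three conditions by three time-points; N = 75 raised to 90 (30 per arm).

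**Assumptions, because the protocol gives no SBR mean, SD, correlation or margin.** Both relaxation arms exceed control by the same amount d, so the standardised means are (0, d, d). A correlation of 0.5 between repeated measures is used where one is needed.

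**Step 1: reproduce the stated N.** For the between-groups test in a repeated-measures ANOVA with m = 3 measures, lambda = f²·N·m / (1 + (m − 1)·rho).
- At N = 75 and rho = 0.5: 0.09 × 75 × 3 / 2 = 10.125. On 2 and 72 df the power is 0.803. So 75 reproduces, and 75 × 1.2 = 90.
- A one-way ANOVA on a single value per person would need 111, and a group-by-time interaction at rho = 0.5 would need 27. Neither gives 75.

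**Step 2: turn f into a relaxation benefit.** With means (0, d, d), f = d·√(2/9).
- One-way reading: d = 0.30 / 0.4714 = 0.636 SD.
- Mean of three measures at rho = 0.5, the reading that reproduces 75: the SD of the mean is √(2/3) of the single-measure SD, so d = 0.636 / 0.8165 = 0.779 SD.

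**Step 3: precision of digital human minus audiotape, unadjusted.** Half-width = t(0.975, 3n − 3)·√(2/n).

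| n per arm | half-width (SD) | share of 0.636 | share of 0.779 |
|---|---|---|---|
| 30 | 1.988 × 0.2582 = 0.513 | 81% | 66% |
| 25 | 1.993 × 0.2828 = 0.564 | 89% | 72% |

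An observed difference of exactly zero at 30 per arm would therefore leave a loss of two thirds to four fifths of the benefit inside the interval.

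**Step 4: chance of a non-significant result when the digital human is truly worse** (noncentral t, 30 per arm).

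| true loss of benefit | benefit 0.636 | benefit 0.779 |
|---|---|---|
| half | 77% | 68% |
| three quarters | 55% | 39% |
| all | 32% | 15% |

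At 25 per arm, a half loss is non-significant 80% (0.636) or 73% (0.779) of the time.

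**Step 5: what an equivalence test could do at 30 per arm** (two one-sided 5% tests, true difference zero, by simulation).
- Half-benefit margin, 0.318 SD (or 0.390 SD on the larger reading): power below 1%.
- Margin 0.55 SD: about 36%. Margin 0.636 SD: about 58%.
- The margin for 80% power is about √(2/30) × (1.663 + 1.282) = 0.76 SD.

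**Step 6: size needed for a half-benefit margin at 80% power** (normal approximation). With a margin of 0.318 SD, equivalence needs 170 per arm and non-inferiority at one-sided 0.025 needs 156. With a benefit of 0.779 SD the figures are 113 and 104.

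**The case against.** **The acceptance rule is inferred.** A reader might conclude that the protocol will accept Hypothesis 2 on p > 0.05. It does not say so. The hypothesis is a prediction, the primary aim is only to investigate the effects of delivery methods, and contrasts, intervals and the wording of null results may be left to an analysis plan not shown here. That stands, and the point does not rest on such a rule. But the hypothesis and the 30 per arm are fixed here, and an analysis plan could add an equivalence test without adding participants.

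**The ANCOVA is planned.** This also stands: the half-widths above are unadjusted. If the covariates explained 10–30% of SBR variance (an assumption), the half-width at 30 per arm would be 0.49–0.43 SD. That is 77–67% of 0.636 SD or 62–55% of 0.779 SD, narrower but still over half the benefit.

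**Equivalence is not impossible.** A reader might infer that 90 participants can never show equivalence within a margin below the relaxation effect. Step 5 shows otherwise: power is about 58% at 0.636 SD and 36% at 0.55 SD, which is low but not zero. On the 0.779 SD reading, the 80%-power margin of 0.76 SD falls just inside the benefit.

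**The Introduction sets no decision rule.** It mentions possible future feasibility work and speaks of delivering relaxation in general, not of SBR. It would be too strong to read it as a go/no-go criterion, or to tie it to a confidence limit with no threshold.

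**Tension among the hypotheses.** Hypothesis 4 expects the digital human to reduce stress more than the audiotape, and Hypothesis 3 has stress mediate SBR, which together suggest an SBR difference. This is a side note and not a contradiction: mediation may be partial, the implied difference small, and the mediation analyses are labelled exploratory.

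**Conclusion.** The point holds. Hypothesis 2 predicts no difference on the primary outcome, and the stated plan can only fail to find one. At 30 per arm the unadjusted 95% interval spans about ±0.51 SD, 66–81% of the benefit implied by f = 0.30 (72–89% at 25 per arm), and a loss of half the benefit would go undetected about 68–77% of the time. Equivalence within half the benefit has almost no power, and 80% power is reached only at a margin of about 0.76 SD.

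These figures assume equal benefit in the two relaxation arms and a benefit of 0.64 to 0.78 SD, the upper value also assuming a correlation of 0.5. Covariate adjustment would improve precision somewhat without changing the conclusion. The defect limits what the trial may conclude about the two delivery methods. It does not affect the comparison of relaxation with control in Hypothesis 1.

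**What to change.** 1. Restate Hypothesis 2 as estimation: the trial will estimate the digital human minus audiotape difference in SBR.
2. Add one line to the Analysis section: report that difference with its 95% confidence interval, unadjusted and from the ANCOVA, beside the relaxation-versus-control effect so that the reader can scale one against the other.
3. State that a non-significant difference will not be reported as no difference or as similarity, and that 90 participants do not give 80% power for equivalence within a margin clearly smaller than the expected relaxation effect.

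If a formal claim of equivalence or non-inferiority is wanted, a justified margin and a sample size to match are needed. For a half-benefit margin that is roughly 104 to 170 per arm on the assumptions above.

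The cost of items 1 to 3 is the wording of Hypothesis 2, one line of analysis and a more modest claim. No extra participants or measurements are required.
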